6.2.4 Progesterone and Pregnancy Monitoring

Treatment Days 19, 21, 23, 25, and 27

- Blood collection for P₄
- Concomitant medication use
- Adverse event and unanticipated adverse device effect assessment
- 12-lead ECG (for subjects who report chest pain or are symptomatic of chest pain)
- LutrePulse Omnipod treatment continues for luteal phase support for subjects with confirmed LH surge

Interview and study drug return

Non-pregnant subjects will visit the site to return used and unused study drug product, their subject diary card and the OmniPod delivery system and report the day menstruation began and duration of menses, if applicable. Gonadotropins for one treatment cycle as well as compensation toward a future IVF cycle could be offered to all non-pregnant subjects who participated in and completed the study (had at least 14 days of study medication) and completed an End-of-Study visit. No study-related follow-up will be conducted regarding such cycles.

14 (+ 4) days after LH surge and 3 days thereafter

Two positive serum pregnancy tests are required to confirm biochemical pregnancy 14 (+ 4) days after LH surge and 3 days thereafter. If only one of the 2 tests is positive, the subject will return within 5 days (unscheduled visit) to confirm pregnancy with another serum pregnancy test. Subjects with 2 negative pregnancy tests will complete an End-of-Study Visit on the day of the second negative pregnancy test.

- Serum pregnancy test
- Concomitant medication use
- Adverse event and unanticipated adverse device effect assessment
- 12-lead ECG (for subjects who report chest pain or are symptomatic of chest pain)

2 to 4 weeks after second positive serum pregnancy test

- TVUS to detect gestational sac and fetal heartbeat
- If fetal heartbeat is not documented, the subject may return within 7 days for another TVUS
- Concomitant medication use
- Adverse event and unanticipated adverse device effect assessment
- 12-lead ECG (for subjects who report chest pain or are symptomatic of chest pain)

End-of-Study Visit

The End-of-Study Visit is performed in conjunction with the final TVUS visit 2 to 4 weeks after the second positive serum pregnancy test or on the day of the second negative serum pregnancy test for subjects who do not become pregnant (2 negative serum pregnancy tests).

- Gynecological examination, including breast exam
- Physical examination, including weight
- Vital signs (blood pressure, heart rate, and oral temperature)
- 12-lead ECG (for subjects who report chest pain or are symptomatic of chest pain)
- Clinical safety laboratory assessment: chemistry, hematology, urinalysis

- Urine pregnancy test (for all except those with documented fetal heart movement)
- Blood collection for P₄ (only for subjects who have discontinued the study and ended treatment on or after Day 14)
- Concomitant medication use
- Adverse event and unanticipated adverse device effect assessment

After the End-of-Study Visit, the site will be asked to provide follow-up information on subjects with a biochemical pregnancy regarding ongoing pregnancy rate and birth data. The follow up will be conducted via telephone or mail. The site will also document miscarriage/pregnancy loss (spontaneous and/or induced), date of live birth, number of deliveries, fetal anomalies, and birth defects.

7 STUDY ASSESSMENTS

7.1 Pharmacodynamic Assessments

Hormone assays will be performed by a central laboratory service. LH will be measured by automated LH two-site sandwich immunoassay using direct chemiluminometric technology (ICMA). Estradiol, progesterone and FSH will also be assayed by a central laboratory service.

A blood sample for E₂, LH and FSH will be taken on Day 1 (pre-treatment baseline) prior to dosing. Additional blood samples for LH and FSH will be taken 5, 15, 30, 60, and 90 minutes after the first dose is administered. The trial site should prepare the subject for at least a 2 to 3-hour office visit.

A blood sample for E₂, LH and FSH will be taken on Day 10 at the same time as the Day 1 first sample (\pm 1 hour) before the first dose is administered by the Day 10 pod. Additional blood samples for LH and FSH will be taken 5, 15, 30, 60, and 90 minutes after the first dose is administered. Samples for measurement of E₂ will also be obtained each time the subject has a TVUS to monitor follicular development and endometrial thickness.

PD blood samples of 10 mL (for LH, FSH, and E₂ levels) will be collected.

Serum samples will be obtained following centrifugation of clotted samples. All serum samples should be clearly labeled before freezing to ensure label adherence to the container and to avoid sample mix up.

All samples will be kept frozen at -20°C and shipped on dry ice. No more than 45 minutes is to elapse between collecting the blood and freezing the serum sample. The subject's number and initials, actual 24-hour clock and date time of each sample collection, sample identification number, and other appropriate information will be recorded on the label and in the eCRF. Any deviations either from the scheduled time of sample collection or from the instructions for handling and processing of samples should be documented in the study records.

Specific instructions for blood collection will be provided in a laboratory manual to the study center.

7.2 Transvaginal Ultrasound

A transvaginal ultrasound, including ovaries, uterus, endometrium, and adnexa, will be performed at Screening (to determine eligibility) and beginning at Day 10 of treatment to monitor number and size of follicles and endometrial thickness. Subjects will return every other day (or based on investigator judgment) for additional TVUS (at least 3 TVUS are to be performed). For subjects that become pregnant, a TVUS will be performed 2 to 4 weeks after the 2nd positive serum pregnancy test.

7.3 Detection of LH Surge

When follicles ≥ 14 mm in mean diameter are detected on TVUS, subjects will begin monitoring LH surge using a Clearblue test. The test will be administered each morning at approximately the same time between 8 and 11 AM. When a positive test result occurs, subjects are to notify the site and will be advised to engage in sexual intercourse on the day of LH surge, the day following LH surge, and per investigator's discretion thereafter.

7.4 Progesterone Evaluations

Blood samples (10 mL) for measurement of progesterone levels will be obtained by venipuncture on Days 19, 21, 23, 25, and 27. A blood sample will also be obtained at the End-of-Study visit for any subject that discontinues the study early and ends treatment on or after Day 14. A P_4 level ≥ 6 ng/mL as measured by a central laboratory indicates ovulation.

7.5 Pregnancy Assessments

7.5.1 Serum Pregnancy Tests

Serum pregnancy tests (β -hCG) will be performed at Screening, and negative pregnancy test results are required for study admission and/or administration of pulsatile GnRH (urine pregnancy tests are performed prior to initial study drug administration for all subjects and at the End-of-Study visit for all subjects except those with documented fetal heart movement). To confirm biochemical pregnancy, a serum pregnancy test will be performed 14 days (+ 4 days) after LH surge and 3 days thereafter. Two positive serum pregnancy tests are required to confirm biochemical pregnancy. If only one of the 2 tests is positive, the subject will return within 5 days (unscheduled visit) to confirm pregnancy with another test. Subjects who have 2 negative serum pregnancy test results will complete their End-of-Study Visit on the day of the second negative serum pregnancy test.

7.5.2 Pregnancy and Pregnancy Outcome

Subjects who achieve pregnancy (2 positive serum pregnancy tests) will be followed up for clinical pregnancy (gestational sac and fetal heart movement) and will complete their final visit (End-of-Study Visit) on the day of documented fetal heart movement on TVUS (2 to 4 weeks after second positive serum pregnancy test).

7.6 Safety Assessments

7.6.1 Medical History

A complete medical/gynecologic history will be obtained at Screening and will include a review of prior medical history and female reproductive status. Documentation of the diagnosis of primary amenorrhea with HH should be provided, including normal or unchanged CT scan or MRI scan of the hypothalamic pituitary region on file and blood samples indicating $FSH < 5$ IU/L and $LH < 5$ IU/L. Medical history findings will be recorded in the eCRF.

7.6.2 Physical and Gynecological Examination

A complete physical examination including height, weight and BMI calculation will be performed at Screening. A gynecological exam including pelvic and breast exam will be performed at Screening. In addition, a Pap smear (or other cervical cancer screening) will also be performed at Screening if not done in the previous 24 months (PAP smear can be performed at Screening, per investigator discretion, even if results within 24 months are available). If done in the previous 24 months, a copy of the report is needed and must be filed in the subject's chart. At the End-of-Study Visit (or at the time of early termination), another physical and gynecological examination including vital signs will be performed. Any clinically significant deterioration from baseline will be recorded as an adverse event.

7.6.3 Vital Signs

At Screening and the End-of-Study Visit, blood pressure, heart rate, and oral body temperature will be measured under resting conditions. All blood pressure measurements should be made using the same arm and prior to any scheduled blood draws.

7.6.4 ECG Evaluation

Subjects who report chest pain or are symptomatic of chest pain should have an ECG evaluation any time during the study when chest pain or symptoms occur.

7.6.5 Clinical Laboratory Tests

7.6.5.1 Hematology, Serum Chemistry, and Urinalysis

A standard panel, as well as the following safety laboratory tests, will be performed at Screening and at the End-of-Study Visit (or at the time of early termination). A 10 hour overnight fast is required prior to collecting the blood samples. The total amount of blood required for safety assessments is approximately 80 mL.

Hematology: red blood cell count, white blood cell count, hematocrit, hemoglobin, platelet count, and differential count.

Serum Chemistry: fasting glucose, blood urea nitrogen, creatinine, potassium, sodium, chloride, calcium, total protein, albumin, total bilirubin, alkaline phosphatase, aspartate aminotransferase, alanine aminotransferase, and gamma glutamyl transferase.

Urinalysis: leukocyte esterase, blood, pH, specific gravity, protein, glucose, urobilinogen, and microscopic if positive for blood or protein.

7.6.5.2 Serological Testing

Serological testing for hepatitis B, hepatitis C, and HIV I and II will be performed at Screening.

7.6.5.3 Hormone Testing

Prolactin (PRL) and TSH will be measured only at Screening. P₄ levels will be measured at Screening and Treatment Days 19, 21, 23, 25, and 27. P₄ levels will also be measured at the End-of-Study visit for any subject that discontinues the study early and ends treatment on or after Day 14. E₂ levels will be measured at Screening, Treatment Days 1 and 10, and each time a TVUS is performed. LH and FSH levels will be measured at Screening and again on Treatment Days 1 and 10 (prior to first dose and 5, 15, 30, 60, and 90 minutes after first dose is administered).

7.6.6 Ovarian Hyperstimulation Syndrome Monitoring

In women undergoing controlled ovarian hyperstimulation, an excessive response to follicular stimulating agents may lead to the development of ovarian hyperstimulation syndrome (OHSS). OHSS represents a spectrum that can be categorized as mild, moderate or severe.

The following table will be used in assessing and classifying the severity of OHSS.

Table 2 Classification of Mild, Moderate and Severe OHSS¹⁷

Mild OHSS	
Grade 1	Abdominal distension and discomfort
Grade 2	Features of grade 1 plus nausea/vomiting and/or diarrhea. Ovaries enlarged to 5-12 cm. ^{a)}
Moderate OHSS	
Grade 3	Features of mild OHSS plus ultrasonic evidence of ascites. ^{b)}
Severe OHSS	
Grade 4	Features of moderate OHSS plus clinical evidence of ascites and/or hydrothorax (or breathing difficulties). Paracentesis due to OHSS symptoms. ^{c)}
Grade 5	All of the above plus change in blood volume, increased blood viscosity due to hemoconcentration, coagulation abnormalities, and diminished renal perfusion and function. ^{d)} Hospitalization due to OHSS symptoms.

- a) For each ovary, the size will be the average of the greatest diameter and its greatest perpendicular diameter. Ovarian enlargement will be based on the average size of the right and left ovaries. The sizes of both ovaries should be recorded.
- b) For subjects with transvaginal evidence of ascites, the size of the fluid pockets in the pelvis (Douglas pouch, vesicouterine pouch, etc.) should be estimated by measuring the greatest diameter and its greatest perpendicular diameter, and multiplying these two numbers (the unit will be cm²). Peritoneal fluid is the total size of all fluid pockets in the pelvis.
- c) In case of paracentesis, the volume of fluid drained should be measured.
- d) Hemoconcentration is defined as hematocrit >45%. Electrolyte disturbances is defined as hyponatremia (sodium <135 mEq/L) and/or hyperkalemia (potassium >5.0 mEq/L). Coagulation abnormalities are defined as presence of thromboembolic events, abnormal prothrombin time or abnormal activated partial thrombin time. Diminished renal perfusion is defined as creatinine >1.2 mg/dl. Oliguria is defined as urine output less than 500 mL / 24 hours. Anuria is defined as failure to produce urine. If applicable, actual volume of urine output will be recorded.

All cases of OHSS will be considered adverse events and will be recorded in the source documents for that subject and on the Adverse Event page in the eCRF. Severe OHSS that requires medical or surgical intervention (i.e., paracentesis, hospitalization, dopamine administration) is considered a serious adverse event (see Section 8.3).

7.7 Concomitant Medications

At each study visit, subjects will be queried for use of any medication other than the study drug since the last visit. Any use of prior medication or concomitant medication, including vitamin or dietary supplements or oral herbal preparations, will be recorded in the source documents and the eCRF and include the following information: name of medication, total daily dose, route of administration, start and stop dates, and reason for use. If the reason for the use of concomitant medication meets the definition of an adverse event, the adverse event should be recorded in the source documents for that subject and on the Adverse Event page of the eCRF.

8 ADVERSE EVENTS AND UNANTICIPATED ADVERSE DEVICE EFFECTS

8.1 Adverse Event Definition

An adverse event is any untoward medical occurrence in a subject participating in a clinical trial. It includes:

- Any unfavorable and unintended sign, symptom or disease temporally associated with the use of the IMP, whether or not considered to be caused by the IMP.
- Adverse events commonly observed and adverse events anticipated based on the pharmacological effect of the IMP.
- Any laboratory abnormality, vital sign or finding from physical or gynecological examination assessed as clinically significant by the investigator [note: findings from assessments and examinations done during screening are not adverse events, but are recorded as medical history.]
- Accidental injuries, reasons for any change in medication (drug and/or dose), reasons for any medical, nursing or pharmacy consultation, or reasons for admission to hospital or surgical procedures.
- Overdoses and medication errors with and without clinical consequences.

8.2 Collection and Recording of Adverse Events

8.2.1 Collection of Adverse Events

The investigator must monitor the condition of the subject throughout the trial from the time of obtaining informed consent until the last visit.

The sources of adverse events cover:

- The subject's response to questions about her health (a standard non-leading question such as "How have you been feeling since your last visit?" is asked at each visit).
- Symptoms spontaneously reported by the subject.
- Investigations and examinations where the findings are assessed by the investigator to be clinically significant changes or abnormalities.
- Other information relating to the subject's health becoming known to the investigator (e.g., hospitalization).

8.2.2 Recording of Adverse Events

The investigator must record all adverse events in the Adverse Event Log provided in each subject's eCRF with information about:

- Adverse event
- Date and time of onset (time can be omitted, if applicable)
- Intensity
- Causal relationship to IMP
- Action taken to IMP
- Other action taken
- Date and time of outcome (time can be omitted, if applicable)
- Outcome
- Seriousness (see 8.3.1 for definition)
- Each of the items in the Adverse Event Log is described in detail in the following sections.

Adverse Event

Adverse events should be recorded as diagnoses, if available. If not, separate signs and symptoms should be recorded. One diagnosis/symptom should be entered per record.

If a subject suffers from the same adverse event more than once and the subject recovers in between the events, the adverse events should be recorded separately. If an adverse event changes in intensity, a worst-case approach should be used when recording the event, i.e., the highest intensity and the longest duration of the event.^a

^a Exception: if an adverse event with onset before the first IMP administration (i.e., a pre-treatment adverse event) changes in intensity, this must be recorded as two separate events. The initial adverse event should be recorded with outcome "not yet recovered" and the date and time of outcome is when the intensity changed. The second adverse event should be recorded with date and time of onset when the intensity changed.

Note the following: A procedure is not an adverse event; the reason for conducting the procedure is. Hospitalization is not an adverse event; the reason for hospitalization is. Death is not an adverse event, but the cause of death is (an exception is sudden death of unknown cause, which is an adverse event).

Date and Time of Onset

The date of onset is the date when the first sign(s) or symptom(s) were first noted. If the adverse event is an abnormal clinically significant laboratory test or outcome of an examination, the onset date is the date the sample was taken or the examination was performed.

Intensity

The intensity of an adverse event must be classified using the following 3-point scale:

Mild: Awareness of signs or symptoms, but no disruption of usual activity.

Moderate: Event sufficient to affect usual activity (disturbing).

Severe: Inability to work or perform usual activities (unacceptable).

Causal Relationship to IMP

The possibility of whether the IMP caused the adverse event must be classified as one of the following:

Reasonable possibility: There is evidence or argument to suggest a causal relationship between the IMP and the adverse event. The adverse event may occur as part of the pharmacological action of the IMP or may be unpredictable in its occurrence.

Examples:

- adverse events that are uncommon but are known to be strongly associated with IMP exposure.
- adverse events that are not commonly associated with IMP exposure, but the event occurs in association with other factors strongly suggesting causation, such as a strong temporal association or the event recurs on re-challenge.

No reasonable possibility: There is no reasonable evidence or argument to suggest a causal relationship between the IMP and the adverse event.

Examples:

- known consequences of the underlying disease or condition under investigation.

- adverse events common in the trial population, which are also anticipated to occur with some frequency during the course of the trial, regardless of IMP exposure.

Action Taken to IMP

The action taken to the IMP in response to an adverse event must be classified as one of the following:

- No change (medication schedule maintained or no action taken)
- Withdrawn
- Dose Interrupted

Other Action Taken

Adverse events requiring therapy must be treated with recognized standards of medical care to protect the health and well-being of the subject. Appropriate resuscitation equipment and medicines must be available to ensure the best possible treatment of an emergency situation.

If medication is administered to treat the adverse event, this medication should be entered in the Concomitant Medication Log.

Date and Time of Outcome

The date and time (time can be deleted/omitted, if not applicable) the subject recovered or died.

Outcome

The outcome of an adverse event must be classified as one of the following:

- Recovered (fully recovered or the condition has returned to the level observed at initiation of trial treatment)
- Recovered with sequelae (resulted in persistent or significant disability/incapacity)
- Recovering
- Not yet recovered
- Fatal

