9.8.2 Adverse Events

Treatment-emergent adverse events (TEAEs) will be tabulated by System Organ Class (SOC) and Preferred Term (PT) using MedDRA for each treatment group. The total number of subjects reporting a TEAE, the percentage of subjects (%) with a TEAE, and the number of TEAEs reported will be presented. A TEAE will be any adverse event occurring after the start of IMP and within 2 days after the last dose, or a pre-treatment adverse event or pre-existing medical condition that worsens in intensity after the start of IMP and within 2 days after the last dose. All adverse events occurring after 2 days from the last dose will be categorized as post-treatment adverse events.

In addition, TEAEs will be presented by causality (relationship to the study medication) and intensity (severity). Deaths, serious adverse events, and adverse events leading to discontinuation will be listed.

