10.2 Adverse Events

An AE is any untoward medical occurrence in a patient or clinical investigation subject administered a pharmaceutical product and which does not necessarily have to have a causal relationship with this treatment.

All Adverse Events (AEs) and unanticipated adverse device effects will be listed, documenting all information as on the eCRF. Verbatim terms of AEs will be coded to the MedDRA preferred terms (PT) and related system organ classes (SOC) using the Medical Dictionary for Regulatory Activities (MedDRA). The latest MedDRA version available at the time of interim analysis or final analysis will be applied.

A treatment emergent adverse event (TEAE) will be any adverse event occurring after start of IMP and within 5 days after the last application, or a pre-treatment adverse event or pre-existing medical condition that worsens in intensity after start of IMP and within 5 days after the last application. All adverse events occurring after 5 days from the last application will be categorized as post-treatment adverse events.

Note: Collection of AEs on the eCRF will begin after the informed consent form (ICF) is obtained from the patient. Any AE prior to the signed ICF will be recorded in the medical history.

Written narratives will be issued for all serious AEs (including deaths) and AEs leading to withdrawal.

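### Footnote a of Protocol 8.2.2 splits a pre-treatment adverse event on any change of intensity, so one that eases after dosing may be counted as treatment-emergent

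*Protocol*

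**What the plan says.** **Recording rule (Protocol 8.2.2).** The general rule is one record per event: "If an adverse event changes in intensity, a worst-case approach should be used when recording the event". Footnote a makes an exception for an event that began before the first IMP administration. If such an event ("a pre-treatment adverse event) changes in intensity, this must be recorded as two separate events") is split, the first record is closed on the date of the change with the outcome *not yet recovered*. For the other record: "The second adverse event should be recorded with date and time of onset when the intensity changed".

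**TEAE definition, Protocol 9.8.2.** The first limb goes by timing: "A TEAE will be any adverse event occurring after the start of IMP and within 2 days after the last dose". The second limb, joined by *or*, is "a pre-treatment adverse event or pre-existing medical condition that worsens in intensity after the start of IMP", within the same window.

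**TEAE definition, SAP 10.2.** The structure is the same. The first limb is "any adverse event occurring after start of IMP and within 5 days after the last application", and the second again requires worsening. The two documents close the window differently, but that does not affect this point.

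Neither document says how to flag the second record of an event that has improved, or that the two records are to be linked.

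**The concern.** The recording rule is triggered by *change* and the second TEAE limb by *worsening*. The two rules were not reconciled. An event that is moderate at screening and eases to mild on Day 3 produces a separate record with a Day 3 onset, and on its face that record meets the first limb. Because the limbs are joined by *or*, the second can add events but cannot remove one that already qualifies by date.

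At stake are the TEAE tables in SAP 10.2.3: subjects with an event, number of events, and the breakdowns by intensity and causality. A recovering screening event could appear there as something new on treatment, with its own intensity and causality rating. Arms are small (about 15 women, SAP Table 1), so single records are visible in the percentages.

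**Working it through.** The plan gives no figure to reproduce. The check sets the rules side by side.

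**Step 1: possible changes of intensity.** Protocol 8.2.2 uses three levels ("The intensity of an adverse event must be classified using the following 3-point scale": mild, moderate, severe). This gives 3 × 2 = 6 ordered changes between two levels:
- 3 worsenings: mild to moderate, mild to severe, moderate to severe
- 3 improvements: the reverse of each

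**Step 2: what each rule does with a change that falls after the first dose and inside the window.**

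| Rule | Worsenings | Improvements |
|---|---|---|
| Footnote a: second record created | 3 of 3 | 3 of 3 |
| TEAE flag from the record's onset date (first limb taken literally) | 3 of 3 | 3 of 3 |
| TEAE flag if the second record is still treated as the pre-treatment event (second limb governs) | 3 of 3 | 0 of 3 |

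The two readings agree on every worsening and disagree on every improvement.

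**Step 3: which women can be affected.** An event must meet all of these conditions:
- It starts after consent and before the first dose. Protocol 8.2.1 and SAP 10.2 collect events from consent. Findings from screening assessments go to medical history (Protocol 8.1).
- It is moderate or severe, because a mild event has no lower grade.
- It persists past the start of dosing on Day 1.
- It then drops a grade without resolving. Resolution is an outcome, not a change of intensity.

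The documents give no rate for this combination, so the expected number cannot be computed.

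**Step 4: effect per woman.** With 15 women in an arm (SAP Table 1), k affected women who have no other TEAE add k/15 to the arm's TEAE incidence. For k = 1 this is 1/15 = 6.7 percentage points. A woman with another TEAE adds to the event count but not to overall incidence, because SAP 10.2.3 counts each subject once per level of summation.

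**Step 5: what the footnote seems to have had in mind.** It closes the first record as *not yet recovered*, although the outcome list in Protocol 8.2.2 also offers *recovering*, which would suit an easing event. It also departs from the section's own rule that onset is when signs or symptoms first appeared. Both choices make sense for a deterioration and little sense for a recovery.

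**The case against.** The strongest reply is that no sentence makes an improving pre-treatment event a TEAE. Both definitions address pre-treatment events by name and admit them only on worsening, and footnote a itself calls the event being split a pre-treatment one. If every second record qualified by date, the worsening limb would have almost nothing left to do for recorded adverse events. A careful programmer could therefore exclude improvements under the present text. This stands in part: inclusion is not a necessary result. It does not settle the matter, because the worsening limb also covers pre-existing medical conditions, which footnote a does not split, so it keeps a purpose even under the literal reading. Two readings that give different counts remain open.

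The other replies mostly stand:
- The eligible events are few (step 3 of the working). The adverse-event row of Protocol Table 1 has no mark at Screening, although collection runs from consent.
- Safety data get no formal testing (Protocol 9.8.1), and the interim decision rules use ovulation rates only (SAP 9).
- Full listings are planned, so the same term reappearing at a lower intensity could be noticed.
- The recording rule is the same in every arm, so nothing in it favours one arm.

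A reader might also infer that the progestin challenge would feed many such events into the tables, since every subject takes medroxyprogesterone for 10 days in screening. The documents do not support that. At least 5 days separate the last tablet from Day 1. If randomization follows that wait (Protocol 3.1) and precedes Day 1 by at least 5 days, or 7 in Canada (Protocol 5.4.1), the gap is at least 5 + 5 = 10 days, or 5 + 7 = 12.

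**Conclusion.** The mismatch is real. Footnote a splits on any change, the first TEAE limb goes by timing, and only the second limb asks for worsening. An onset-date algorithm would count 3 kinds of improvement that the definitions evidently did not mean to count.

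The size is limited. The number of women is unknown and probably small. Each one without another TEAE moves a 15-woman arm by 6.7 points, in a descriptive table. That figure assumes the planned 15 treated women per arm.

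Two stronger conclusions might be inferred, and neither follows. One is that an easing event necessarily becomes a TEAE; the worsening limb permits a reading that excludes it. The other is that the safety comparison between doses is materially distorted; the documents give no rate from which to show this, and the primary analysis is untouched. This is a specification gap worth closing before database lock because it is cheap to close and can change counts.

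**What to change.** Add to SAP 10.2: *A second record created under footnote a of Protocol 8.2.2 is treatment-emergent only if it falls within the TEAE window and its intensity is higher than that of the preceding pre-treatment record. The two records are matched by subject, by term, and by the outcome date of the first being equal to the onset date of the second.*

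The date match works because the footnote sets both dates to the time of the change. True worsenings remain TEAEs. So does an event that first eases and later exceeds its pre-treatment grade, since the second record then carries its worst intensity under the general rule. If no pair can be matched, the record should stay under the onset-date rule and be listed for review.

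The SAP is the right place for this. First subject first visit was planned for March 2014, so records made under the present footnote may already exist, and a new recording rule would not reach them. Aligning *changes* with *worsens* in footnote a is optional and can wait for the next protocol amendment.

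Cost: one sentence and a small matching step, because the items listed for the adverse event log in Protocol 8.2.2 include no link field. No new data are needed.
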